4.2. METHOD OF TREATMENT ASSIGNMENT

Upon eligibility confirmation, subject randomization will occur at Day 0 prior to receiving treatment by randomly selecting an envelope containing cohort assignment. Randomization envelopes will be divided into two categories: one for subjects with vision measuring 20/50 or better, and one for subjects with vision

measuring worse than 20/50. Subjects with vision measuring 20/50 or better will be randomized in a 1:1:1 fashion in order to minimize the chance of an accidentally skewed population of patients with good vision in one treatment group. Subjects with vision measuring worse than 20/50 will be randomized in a 1:2:2 fashion. Subjects will be randomized into 1 of the following 3 cohorts:

- **Cohort A:** Subjects receive monthly treatment of 0.5 mg IVT ranibizumab for 48 weeks. Beginning at week 52, all subjects will enter a treat and extend protocol for IVT ranibizumab retreatment.
- **Cohort B:** Subjects receive monthly treatment of 0.5 mg IVT ranibizumab for 48 weeks. 1 week (\pm 3 days) after the initial dose of IVT ranibizumab is delivered, the subject will have peripheral targeted-retinal photocoagulation (TRP) to areas of peripheral retinal ischemia based on 120° or greater wide field angiography that was performed at the screen visit. After the first session of TRP, subjects will have a repeat wide field angiogram at Week 24 and Week 36 and will receive additional TRP as needed (PRN) to areas of peripheral retinal ischemia. Beginning at week 52, all subjects will enter a treat and extend protocol for IVT ranibizumab retreatment.
- **Cohort C:** Subjects will receive a loading dose (3 consecutive monthly doses) of 0.5 mg IVT ranibizumab followed by PRN treatment with 0.5 mg IVT ranibizumab. 1 week (\pm 3 days) after the initial dose of IVT ranibizumab is delivered, the subject will have peripheral targeted-retinal photocoagulation (TRP) to areas of peripheral retinal ischemia based on wide field angiography that was performed at the screen visit. After the first session of TRP, subjects will have a repeat wide field angiogram at Week 24 and Week 36 and will receive additional TRP as needed (PRN) to areas of peripheral retinal ischemia. Beginning at week 52, all subjects will enter a treat and extend protocol for IVT ranibizumab retreatment.

4.3. STUDY TREATMENT

4.3.1. Formulation of Ranibizumab

Ranibizumab is formulated as a sterile solution aseptically filled in a sterile, 3 mL stoppered glass vial. Each single-use vial is designed to deliver 0.05 mL of 10 mg/mL ranibizumab aqueous solution with 10 mM histidine HCl, 10%, β -trehalose dihydrate, and 0.01% polysorbate 20, pH 5.5, which results in the delivery of a 0.5 mg dose of ranibizumab. Each vial contains no preservative and is suitable for **single use only**.

Further details and molecule characterization will be included in the Investigator Brochure.

4.3.2. Dosage, Administration, and Storage of Ranibizumab

4.3.2.1. Dosage

Subjects will receive intravitreal injections of 0.5 mg ranibizumab according to their specific cohort treatment schedule.

Ranibizumab retreatment criteria for Cohort C, will be based on:

- On SD-OCT, recurrent or persistent fluid
- Treating physician discretion based on clinical evaluation/finding

4.3.2.2. Administration

*See Appendix B for detailed injection procedures.

4.3.2.3. Storage

Upon receipt, study drug kits should be refrigerated at 2°C - 8°C (36°F - 46°F). DO NOT FREEZE. Do not use beyond the expiration date.

Ranibizumab vials should remain refrigerated. Protect vials from direct light. Store in original carton until time of use.

RANIBIZUMAB VIALS ARE FOR SINGLE USE ONLY. Vials used for one subject may not be used for any other subject.

4.3.3. Peripheral Targeted Retinal Photocoagulation (TRP)

Subjects in cohort B and C can receive up to 3 sessions of TRP, based on evidence of peripheral ischemia on wide-field fluorescein angiogram. Areas of peripheral ischemia will be selectively treated, preserving areas of more perfused retina. This will minimize any visual acuity loss secondary to non-selective, pan-retinal photocoagulation.

*See Appendix C for TRP administration procedures and PRN retreatment criteria.

4.4. CONCOMITANT AND EXCLUDED THERAPIES

Subjects may continue to receive all medications and standard treatments administered for their systemic conditions at the discretion of their treating physician.

During the 104 week study period, only the treatments mandated by each cohort will be permitted for the study eye. The fellow eye may receive all medications and standard of care therapies necessary.

4.5. STUDY ASSESSMENTS

4.5.1. Assessments during the Treatment Period

*Refer to Appendix A for a schedule of study assessments.

4.5.1.1. Safety Procedures

Vital Signs (Performed at every visit)

Vital signs will include measurements of pulse and systolic and diastolic blood pressure while the subject is in a seated position. Vital signs should be taken pre-dose at every visit.

B-Scan (Performed at Screen, Week 48, and Week 104, if applicable)

B-scans will be performed, at the discretion of the investigator, three times during the study to ensure the lesion (if any is present) is unchanged. B-scans should be performed per standard of care by qualified site personnel and evaluated by the PI or Sub-Investigators.

4.5.1.2. Efficacy Procedures

Best Corrected Visual Acuity (Performed at every visit)

Visual function of the study eye and fellow eye will be assessed using the ETDRS protocol (The Early Treatment Diabetic Retinopathy Study Group, 1985) at 4 meters at every visit.

**See Appendix H for Visual Acuity Testing Protocol*

Intraocular Pressure (Performed at every visit)

Intraocular pressure (IOP) of both eyes will be measured pre-dose at every visit. IOP of the study eye will be measured 30 minutes (\pm 15 minutes) post-dose. The method used for IOP measurement for a subject must remain consistent throughout the study.

Slit Lamp Examination (Performed at every visit)

Subject's anterior eye structure and ocular adnexa of both eyes will be examined at every visit using a slit lamp, pre-dose, by the PI or Sub-Investigator.

Indirect Ophthalmoscopy (Performed at every visit)

Subject's posterior pole and peripheral retina will be examined by indirect ophthalmoscopy at every visit, pre-dose by the PI or Sub-Investigator.

Optical Coherence Tomography (OCT) (Performed at every visit)

Ocular morphology will be evaluated at every visit using the Heidelberg Spectralis SD-OCT. Starting with the screening visit, images will be captured for both eyes. All OCTs will be electronically archived at the site as part of the

source documentation. Optical coherence tomography technicians must provide previous certification by a reading center, within the last 2 years, or provide evidence of proper training to ensure consistency and quality in image acquisition.

*See Appendix D for OCT protocol

Fundus Photography/Fluorescein Angiography

The anatomical state of the retinal vasculature will be evaluated using Fundus Photography (FP) and wide field Fluorescein Angiography (FA). FP and FA will be captured for both eyes. All FPs and FAs will be archived at the site as a part of source documentation. Photographers must provide previous certification by a reading center, within the last 2 years, or provide evidence of proper training to ensure consistency and quality in image acquisition.

FP and FA evaluations will be performed at screening, Week 24, Week 36, Week 48, Week 78, and Week 104 or Early Termination visit.

* See Appendix D for Imaging Protocol

4.5.2. Early Termination Assessments

Subjects who withdraw from the study prior to completion should return for an early termination evaluation 28 days (\pm 7 days) following the last injection/study visit for monitoring of all adverse events (serious and nonserious). The schedule of assessments for early termination is the same as that for the final visit.

4.6. SUBJECT DISCONTINUATION

Subjects have a right to withdraw from the study at any time.

The subject may be withdrawn from the study for any reasons: if it is in the best interest of the subject, concurrent illness, adverse events, or worsening condition. Retina Consultants of Houston or the Principal Investigator may request the withdrawal of a subject because of protocol violations, administrative reasons, or any other valid and ethical reasons.

If a subject discontinues from the study, he or she will not be allowed to re-enter the study.

Reasons for subject discontinuation may include, but are not limited to, the following:

- Sensory rhegmatogenous retinal detachment or Stage 3 or 4 macular hole
- Investigator determination that it is not in the best interest of the subject to continue participation

- Pregnancy
- Need for anti-VEGF therapy other than ranibizumab in the study eye, unless as a part of the prospective investigational study design
- SAE
- Any other safety concerns

In the event of an adverse event in the study eye that is considered by the investigator to be severe in intensity, serious consideration should be given to discontinuing the subject from the study.

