3.4. SAFETY PLAN

The safety assessments to be conducted for this study are listed in Section 4.5.

The safety and tolerability of intravitreal ranibizumab injections have been investigated in previous Phase I, I/II, III, and IIIb studies in AMD, RVO, and DME trials. Potential safety issues associated with the route of administration or the pharmacology of ranibizumab in the study population include decreased BCVA, intraocular inflammation, intraocular infection, transient and/or sustained elevation of intraocular pressure (IOP), cataract development or progression, retinal or intravitreal hemorrhage, macular edema, retinal break or detachment, and arterial thromboembolic events (ATEs). Safety will be assessed by visual acuity, ophthalmic examinations, fluorescein angiograms, B-Scans, OCT, intraocular pressure, vital signs, and adverse event documentation.

To minimize the risks of intraocular infections, all injections will be performed employing sterile techniques as described in Appendix B. Study drug administration will be held for subjects who experience certain ocular events or infections. In the event any subject develops an adverse event in the study eye that is considered by the evaluating physician to be severe in intensity, serious consideration should be given to withdrawing the subject from the study.

The PI or designated Sub-Investigators will review all adverse events on an ongoing basis to determine causality and relationship to study drug and/or study procedures.

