6. ANALYSES

All outcomes will be presented using descriptive statistics. For comparison of groups for primary and secondary outcomes, variables of interest will be statistically analyzed using analysis of variance (ANOVA), Student's t-tests, Chi square and Fisher's exact test. ETDRS data will be obtained for all visits

for all 40 of the participants. Bonferroni correction was applied to all pairwise comparison analyses for this study.

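### Withdrawal from the study is the only permanent exit described, so week-48 and week-104 acuity can be lost for outcome-related reasons, contrary to the SAP's statement of complete ETDRS data

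*Protocol*

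**What the plan says.** - **Grounds.** Protocol 4.6 allows withdrawal from the study for reasons it gives as "in the best interest of the subject, concurrent illness, adverse events, or worsening condition". The sponsor or principal investigator "may request the withdrawal of a subject because of protocol violations, administrative reasons" or for other valid reasons. A non-exhaustive list adds, among others, "Sensory rhegmatogenous retinal detachment or Stage 3 or 4 macular hole", SAE, and need for a different anti-VEGF drug. A discontinued subject cannot come back.
- **Severe study-eye adverse event.** Protocol 3.4 says that "serious consideration should be given to withdrawing the subject from the study". Section 4.6 and SAP 4.3 say much the same. Section 3.4 and SAP 4.3 also provide for study drug to be held after certain ocular events or infections, without giving criteria or a visit schedule.
- **After withdrawal.** Protocol 4.5.2: "Subjects who withdraw from the study prior to completion should return for an early termination evaluation 28 days" (± 7 days) after the last injection or study visit. The assessments are those of the final visit, and the Week 104 column of Appendix A includes BCVA.
- **Analysis.** The primary outcome is mean change in ETDRS acuity from Day 0 to weeks 48 and 104 (Protocol 4.8.3.1, SAP 6.1). Protocol 4.8.4 uses available cases and does not impute.
- **Completeness.** SAP 6 states that "ETDRS data will be obtained for all visits" for all 40 participants. The SAP has no missing-data section.

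**The concern.** Neither document lets a subject stop injections or laser for good and still attend weeks 48, 78 and 104. Stopping permanently is described only as leaving the study.

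Some of the grounds overlap with what the trial measures. Section 5.1 counts new signs or symptoms of radiation retinopathy as adverse events. Section 5.6 treats an event that costs more than 30 letters, against the most recent BCVA, as a serious ocular event. Section 4.6 lists SAE as a possible reason to discontinue. A large fall in acuity can thus itself become a listed reason for ending follow-up. The choice is discretionary, and section 4.2 describes no masking of the investigators who make it.

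If such subjects leave, the available-case mean at weeks 48 and 104 is taken over the eyes that stayed. The endpoints of 15-letter loss and of avoiding neovascular glaucoma or vitreous hemorrhage are exposed in the same way. Monthly injection applies to Cohorts A and B and laser to B and C, so treatment-related withdrawal need not be equal across cohorts. With planned sizes of 8, 16 and 16, one or two eyes matter.

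**Working it through.** The plan gives no figure on this point to reproduce. The SAP's sample size (41 needed, 40 taken) states no effect size, SD or dropout rate. Back-solved with the noncentral F for three groups, 41 at 80% power implies Cohen's f = 0.504, with no stated allowance for loss.

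**Tracing one withdrawal through the text**

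1. A subject withdraws after the week 16 visit (4.6). No return is possible.
2. The early-termination visit falls at about week 16 + 4 = week 20 (4.5.2). It would coincide with an analysis time only if the last visit were near week 44 (44 + 4 = 48) or week 100 (100 + 4 = 104).
3. BCVA is recorded at that visit, but Protocol 4.8 and SAP 6 do not say how the value enters the week-48 or week-104 comparison. Under 4.8.4 the subject is absent from both.
4. SAP 6 assumes ETDRS data at every visit for all 40. A single such withdrawal makes that untrue, and 4.8.4 already expects missing values. This conflict needs no assumption about how many subjects leave.

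**Possible size**

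Inputs from the documents: cohort sizes 8, 16 and 16. These are planned sizes; the 1:1:1 stratum for 20/50 or better can shift them. Assumptions, because the documents give no values: normally distributed changes, SD of 10, 15 or 20 letters, and the number of eyes lost.

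Let M be the mean change of all n eyes, L the mean of the m lost eyes and R the mean of those retained. From nM = mL + (n − m)R,

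R − M = [m / (n − m)] × (M − L).

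If loss is unrelated to acuity, M − L is zero on average and there is no shift. The other extreme is that the m lost eyes are the m worst. Simulation of that case (400,000 samples per cohort size) gives:

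| n | m lost | Shift (SD) | SD 10 | SD 15 | SD 20 |
|---|---|---|---|---|---|
| 16 | 1 | 0.118 | 1.2 | 1.8 | 2.4 |
| 16 | 2 | 0.218 | 2.2 | 3.3 | 4.4 |
| 8 | 1 | 0.203 | 2.0 | 3.1 | 4.1 |
| 8 | 2 | 0.379 | 3.8 | 5.7 | 7.6 |

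The last three columns are letters. In the second row, 0.218 = (2/14) × (M − L), so the lost eyes lie 0.218 × 7 = 1.53 SD below the cohort mean. If they lay half as far below, the shift would halve to 0.109 SD, or 1.1 to 2.2 letters.

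With no true difference between cohorts, one-way ANOVA at a nominal 5% (20,000 simulated trials per pattern) rejected in 4.9% of trials with no loss, 9.7% if only C lost its worst 2, 10.3% if only A lost its worst 2, and 11.8% if B and C each lost their worst 2.

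**The case against.** The case against making much of this is substantial, and most of it stands as a limit on the point.

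- A reader might infer that the protocol sends every SAE, detachment, worsening eye or protocol violation out of the study. It does not. Section 4.6 is permissive throughout; 3.4 and SAP 4.3 concern only severe study-eye events and ask only for consideration. A worsening eye may stay to week 104.
- A reader might infer that the worst eyes' acuity is never collected. BCVA is taken at every visit and again at early termination. What can be missing is the value at week 48 or 104, and a subject withdrawn after week 48 loses only week 104.
- A reader might infer that no analysis could help. Pre-withdrawal and termination acuities can support sensitivity analyses, though these rest on assumptions about what happened afterwards.
- Not every interruption is an exit: study drug can be held, and Cohort C attends visits without injection when retreatment criteria are not met.
- Worsening condition is undefined and need not mean vision. Protocol violations and administrative reasons may be unrelated to acuity. No dropout rate is documented, overall or by cohort.
- The 5-letter figure in Appendix E is no yardstick for these shifts. It is a retreatment trigger for one eye, measured from the previous visit and requiring SD-OCT evidence.

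These points do not remove the gap. No continued follow-up is described after permanent discontinuation, the termination acuity has no analytic role, and the SAP statement still conflicts with Protocol 4.5.2, 4.6 and 4.8.4.

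**Conclusion.** The point holds in a limited form. Two parts rest on the text alone: withdrawal is the only permanent exit described, followed by one visit; and the SAP's claim of complete ETDRS data conflicts with the rules on withdrawal and missing data.

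The bias is a possibility, not a finding. It requires that subjects actually leave, that their acuity differs from that of subjects who stay, and, for the between-cohort comparison, that this happens unevenly. If the worst 2 of 16 eyes were lost, a cohort's mean change would rise by about 0.22 SD, or 2.2 to 4.4 letters for an assumed SD of 10 to 20. That is an upper bound for two lost eyes; loss unrelated to acuity would give no shift on average. The amendment is worth making because it is cheap and the cohorts are small.

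**What to change.** - **Protocol 4.5.2 and 4.6, consistently with 3.4 and SAP 4.3:** distinguish stopping study injections or laser from withdrawal from the study. State that subjects who stop treatment without withdrawing consent are asked to attend the remaining week 48, 78 and 104 visits for BCVA, SD-OCT, adverse events and a record of study-eye treatments received.
- **Protocol 4.4 and 5.2.1:** reconcile with this. Section 4.4 permits only cohort-mandated study-eye treatment throughout the 104 weeks. Section 5.2.1 closes general adverse event reporting 28 days after the last treatment or at discontinuation.
- **SAP 6:** replace the completeness sentence with one saying that week-48 and week-104 ETDRS data are sought for all randomised subjects regardless of treatment status, with off-treatment values flagged.
- **If follow-up is already complete** (SAP 2.1 is written in the past tense, so this is possible): missed visits cannot be restored. Correct the SAP 6 sentence, report withdrawals by cohort, reason and last acuity, and add a sensitivity analysis using the early-termination acuity.

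The clinical grounds for stopping treatment are not changed. The cost is an amendment and up to three already scheduled visits for each subject who stops treatment. The downside is that some values will be taken off treatment or after other therapy and will need care in interpretation.

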4.7. STUDY DISCONTINUATION

Retinal Consultants of Houston or Genentech may terminate this study at any time. Reasons for terminating the study may include the following:

- The incidence or severity of adverse events in this or other studies indicates a potential health hazard to subjects
- Subject enrollment is unsatisfactory
- Data recording is inaccurate or incomplete

4.8. STATISTICAL METHODS

4.8.1. Analysis of the Conduct of the Study

40 subjects from 4 sites in the United States will be enrolled. Eligible subjects who have provided informed consent will be screened for eligibility before the initiation of any study procedures. Screening evaluations may be performed at any time within 0 – 14 days preceding Day 0. These subjects must have radiation retinopathy with activity seen on SD-OCT, FP or FA.

*See Appendix A, the study flow chart, for screening assessments.

4.8.2. Safety Analysis

Any adverse events, laboratory assessments, physical examinations, vital signs, ocular examinations and measurements from all 40 subjects will be utilized to summarize safety data for this study.

4.8.3. Efficacy Analyses

4.8.3.1. Primary Endpoint

- Mean change in ETDRS visual acuity at week 48 and week 104 from Day 0.

4.8.3.2. Secondary Endpoints

- The mean number of intravitreal injections required per subject per cohort.

- Percentage of subjects with persistent macular edema, based on SD-OCT, at week 48 and week 104 compared to Day 0.
- Percentage of subjects avoiding the development of neovascular glaucoma and/or vitreous hemorrhage.

4.8.3.3. Additional Endpoints

- Percentage of subjects with persistent leakage on FA at week 48 and week 104
- Mean change in foveal thickness per SD-OCT from Day 0 to week 48 and week 104
- Percentage of subjects who experience a gain of 1 or 2 lines in ETDRS BCVA, VA of $\geq 20/40$ and VA of $\leq 20/200$ at week 48 and week 104
- Percentage of subjects who experience a loss of 15 or more letters in ETDRS BCVA from Day 0 to week 48 and week 104

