4.8.4. Missing Data

Analyses of efficacy and safety will be based on available cases, without imputation for missing values.

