5.1. ADVERSE EVENTS

An AE is any unfavorable and unintended sign, symptom, or disease temporally associated with the use of an investigational medicinal product (IMP) or other protocol-imposed intervention, regardless of attribution.

This includes the following:

- AEs not previously observed in the subject that emerge during the protocol-specified AE reporting period, including signs or symptoms associated with radiation retinopathy that were not present prior to the AE reporting period.
- Complications that occur as a result of protocol-mandated interventions (e.g., endophthalmitis).

Preexisting medical conditions (other than the condition being studied) judged by the investigator to have worsened in severity or frequency or changed in character during the protocol-specified AE reporting period.

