6.1 Primary Outcome

The primary analysis will compare cohorts (A vs. B vs. C) on their mean change in ETDRS BCVA from baseline to week 48 and week 104 with the above described statistical tests. Adverse events will be reported using counts and percentages for each cohort.

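### The SAP does not carry over the protocol's 15-letter-loss percentage, and no rule says whether eyes that leave early would count in it

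*Protocol*

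**What the plan says.** **The endpoint.** Protocol 4.8.3.3 lists among the additional endpoints "Percentage of subjects who experience a loss of 15 or more letters in ETDRS BCVA from Day 0 to week 48 and week 104". Nothing in either document withdraws it.

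**The SAP on acuity.** The primary analysis (SAP 6.1) compares the cohorts "on their mean change in ETDRS BCVA from baseline to week 48 and week 104". SAP 6.2 covers macular thickness, exudates, hemorrhage, neovascularization, injection frequency and the correlation of injection frequency with thickness or acuity. Adverse events are reported as counts and percentages by cohort. There are also two general commitments: SAP 4.3 names visual acuity among the safety assessments, and section 6 promises descriptive statistics for all outcomes. Neither gives a loss threshold.

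**The safety data set.** Protocol 4.8.2 says that "ocular examinations and measurements from all 40 subjects will be utilized to summarize safety data for this study".

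**Missing values and early leavers.** Protocol 4.8.4 says: "Analyses of efficacy and safety will be based on available cases, without imputation for missing values". Protocol 4.6 allows withdrawal for "concurrent illness, adverse events, or worsening condition". Protocol 4.5.2 asks leavers to return for an evaluation and adds: "The schedule of assessments for early termination is the same as that for the final visit". Appendix A schedules BCVA at week 104, so acuity is due at early termination too. The SAP has no missing-data rule. Its section 6 says "ETDRS data will be obtained for all visits", for all 40 participants.

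**The concern.** Decreased BCVA is the first potential safety issue named in both protocol 3.4 and SAP 4.3. With 8 or 16 eyes per cohort, the number that lost substantial vision is a natural safety figure, and the protocol already defines it. The SAP, which should say how it will be produced, does not mention it.

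Copying the endpoint across would not be enough. It is tied to two fixed visits, and the available-case rule covers safety as well as efficacy. An eye that worsens, is withdrawn and has no week-48 value is not in the week-48 row, even if its loss was recorded at early termination. Those are the eyes a safety reader most wants to see.

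**Working it through.** **1. Look for the endpoint in the SAP.** The documents state no figure for this endpoint, so the first check is a side-by-side reading.

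| SAP section | Content on acuity | 15-letter loss? |
|---|---|---|
| 3.1, 4.1, 6.1 | mean change at weeks 48 and 104 | no |
| 3.2, 4.2 | none | no |
| 4.3 | acuity named as a safety assessment | no threshold |
| 6 | descriptive statistics for all outcomes; names the tests | no |
| 6.2 | correlation with injection frequency | no |

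The other acuity categories in protocol 4.8.3.3 (line gains, 20/40 or better, 20/200 or worse) are absent as well.

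**2. Would adverse event counts replace it?** In part. Protocol 5.1 counts as adverse events new findings, "including signs or symptoms associated with radiation retinopathy that were not present prior to the AE reporting period". Protocol 5.6 has seriousness criteria with no letter threshold, such as a possible need for intervention to prevent permanent loss of sight. The one letter threshold is a drop of more than 30 letters, measured from the most recent assessment and not from Day 0. An eye losing 3 letters at each of 12 visits is down 12 × 3 = 36 letters without ever meeting it. Such an eye may still be reported under another criterion, but nothing guarantees a count of 15-letter losses from Day 0.

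**3. What the fixed-visit count can miss.** Cohort sizes of 8, 16 and 16 come from SAP section 2. Numbers of losers and leavers are assumptions.

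Suppose 2 of 16 eyes lose 15 or more letters and leave before week 48, and none of the other 14 does. Intervals are exact (Clopper-Pearson) 95%.
- Week-48 row: 0/14 = 0%, upper limit 1 − 0.025^(1/14) = 23.2%.
- Last-available row: 2/16 = 12.5%, interval 1.6% to 38.3%.

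More generally, take n eyes, d leavers and x losers seen at the visit. The available-case percentage is x/(n − d). Over all randomized eyes the true figure lies between x/n (no leaver lost 15 letters) and (x + d)/n (every leaver did).

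| n | x | d | x/(n − d) | x/n to (x + d)/n |
|---|---|---|---|---|
| 8 | 1 | 1 | 1/7 = 14.3% | 12.5% to 25.0% |
| 8 | 1 | 2 | 1/6 = 16.7% | 12.5% to 37.5% |
| 8 | 1 | 4 | 1/4 = 25.0% | 12.5% to 62.5% |
| 16 | 2 | 2 | 2/14 = 14.3% | 12.5% to 25.0% |
| 16 | 2 | 3 | 2/13 = 15.4% | 12.5% to 31.2% |

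Early termination values narrow these ranges for every leaver who attends that visit.

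**4. Precision of the proposed rows.** With no losers the exact upper 95% limit is 1 − 0.025^(1/n): 36.9% for 0/8 and 20.6% for 0/16.

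**5. Measurement noise in a single-visit row.** The documents give no test-retest SD. Assume independent normal errors with a per-visit SD of 4 to 6 letters, so that the change from Day 0 in a stable eye has SD × √2. The chance of an apparent 15-letter loss is Φ(−14.5/(SD√2)): 0.5% at SD 4, 2.0% at SD 5 and 4.4% at SD 6. This applies alike to week 48, week 104 and the last available visit.

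**The case against.** The strongest reply is that little is missing. The endpoint sits in the protocol's own statistical methods section, with threshold, baseline and visits defined, and a short SAP that does not repeat a third-tier endpoint has not cancelled it. That stands. A reader might infer that the endpoint was abandoned; the documents do not say so.

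The SAP is also not silent on acuity as safety. Its sections 4.3 and 6, read with protocol 4.8.2, promise some descriptive acuity summary from all 40 subjects. That stands too, and limits the criticism to the absence of a threshold and of a rule for early termination values.

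One might go further and say that reporting mean change conceals vision loss. For example, 2 of 16 eyes losing 30 letters while 14 gain 60/14 = 4.3 gives a mean of 0. But any SD or range would expose this (SD 11.7, minimum −30), and the SAP promises descriptive statistics, though without listing which. The example would hold only for a bare mean.

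Finally, a reader might infer that the plan expressly excludes early termination acuity. It does not: available cases are never defined, and neither document says how those values are assigned. On its ordinary meaning the rule leaves out an eye with no week-48 value, but the defect is a missing rule, not a stated exclusion. Nor do the documents show that such withdrawals will be common, since no rate is given.

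**Conclusion.** The concern holds as a minor point about safety reporting. The SAP does not carry over an acuity-loss endpoint that the protocol still contains, and neither document says how acuity at early termination enters an acuity-loss summary. The first gap alone is missing detail. The second gives the point its substance, because a fixed-visit count can leave out eyes that worsened and left: 0/14 instead of 2/16 in the example.

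That size is illustrative. It rests on assumed numbers of losers and leavers and on leavers attending the early termination visit. The absence of the endpoint from the SAP, the available-case rule, the permission to withdraw for worsening and the scheduled early termination acuity are all on the page. A reader might infer that the primary result is compromised; this point does not support that. It changes neither the primary comparison nor the sample size.

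**What to change.** In SAP 4.3 and section 6, add one descriptive table by cohort, with no hypothesis test. Give the number and percentage of study eyes that lost at least 15 letters from Day 0:

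- at week 48;
- at week 104;
- at the last available visit, including early termination.

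State the number of eyes contributing to each row. The other acuity categories in protocol 4.8.3.3, including 20/200 or worse, can go in the same table.

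The cost is one table from acuity already scheduled at every visit and at early termination. Parts of the SAP are in the past tense; if analysis has begun, the table can still be made from data already collected. It has three limits. Intervals are wide, as shown above. The last-available row mixes follow-up times, which the row label should say. Each row carries some measurement noise, about 0.5% to 4.4% chance losses in stable eyes under the assumed SDs.
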